7 RESEARCH QUESTION AND OBJECTIVES, ENDPOINTS, AND VARIABLES

The proposed study will address the following questions:

The overall objectives of this study are to retrospectively evaluate the safety and effectiveness of osilodrostat in the treatment of non-CD CS in France and to characterise clinical parameters of CS patients treated with osilodrostat.

The proposed study will address the following research questions:

- What are the safety and effectiveness of osilodrostat in the management of non-CD CS patients in a real-world setting?
- What is the cohort demography, and how do clinical characteristics change with osilodrostat treatment?
- How is osilodrostat dosed and titrated in this patient cohort?
- What are the outcomes in these patients, including long term?
- How are these patients monitored (i.e., biochemically, and follow up characteristics)?
- What is the incidence of overall treatment-emergent adverse events (TEAEs) and adverse events of special interest (AESI)?

Table 1 Design Elements

	Objective	Endpoint	Variable
Primary	To estimate the	Number and Proportion of	Mean Urinary free
	effectiveness of	patients with mean urinary	cortisol (mUFC)
	osilodrostat in	free cortisol (mUFC)	
	the treatment of	≤upper limit of normal	
	non-CD	(ULN) at 12 weeks	
	Cushing's		
	Syndrome (CS)		

LCI699-RECAG-NI-059	96
•	

	Objective	Endpoint	Variable
Secondary Secondary	To assess the long-term effects of osilodrostat in the treatment of non-CD Cushing's Syndrome (CS) To assess the	Proportion of patients with mUFC ≤ ULN at weeks 24, 36 and every 12 weeks thereafter. Change from baseline for	mUFC mUFC; morning serum
Secondary	change in biochemical variables associated with osilodrostat treatment in non-CD CS patients	biochemical variables to Week 4, 8, 12, 18, 24, 36, and to every 12 weeks until the earlier of loss to follow-up, death, or the end of the retrospective follow-up period or treatment discontinuation	cortisol (normal and abnormal values as per standard definition)
Secondary	To assess actual and change in clinical outcomes associated with osilodrostat treatment in non-CD CS patients	Actual and percent Change in BMI, ECG, blood pressure, metabolic, biochemical, and hormone levels from baseline for clinical outcomes to Week 4, 8, 12, 18, 24, 36, and to every 12 weeks until the earlier of loss to follow-up, death, or the end of the retrospective follow-up period or treatment discontinuation	Body Mass Index (BMI), electrocardiogram (ECG), Co-morbidities, Blood pressure, CS- specific physical exam findings Laboratory abnormalities (sodium, potassium, calcium levels, CO ₂ , glucose, Glycated haemoglobin (HBA1c), lipids), and hormones including: Plasma ACTH Serum 11- Deoxycortisol Plasma 11- Deoxycorticosterone Plasma Aldosterone, Plasma Renin Total Serum Testosterone or oestradiol per patient sex Serum LH Serum FSH

LC1079-KECAC	CONTIDENTIAL		
	Objective	Endpoint	Variable
	To characterise initiating doses, up- and downtitration regimens for non-CD CS patients treated with osilodrostat	Change from initial dose	Dose
	To estimate the incidence of overall treatment-emergent adverse events (TEAEs) and adverse events of special interest (AESI) for non-CD CS patients treated with osilodrostat	Proportion of patients who experienced TEAE and AESI	TEAE overall; TEAE specific to CS; AESI, Comprehensive metabolic panel (CMP), Complete blood count (CBC)
Exploratory	To assess change in late night salivary cortisol level from baseline to various timepoints for non-CD CS patients treated with osilodrostat	Proportion of patients with normal late night salivary cortisol at Week 4, 8, 12, 18, 24, 36, and at every 12 weeks until the earlier of loss to follow-up, death, or the end of the retrospective follow-up period or treatment discontinuation	Late night salivary cortisol

8 RESEARCH METHODS

8.1 Study Design

This is a multi-centre, observational, non-comparative, retrospective cohort study designed to evaluate the long-term safety and effectiveness of osilodrostat in non-CD CS patients. Patients treated with oral osilodrostat regardless of the duration of their treatment will be followed retrospectively for up to 36 months after initiating osilodrostat. Follow-up for each patient will be variable, rather than fixed. Using a variable follow-up, rather than a fixed follow-up period for each patient, maximises the

Final v2.0 33 of 63 18 April 2023

person-time of patient follow-up in the study. This methodological approach allows for increased precision of findings compared to a fixed follow-up period because the unit of observation in analyses is person-time accrued aggregately across all eligible patients, rather than a count denominator of patients exposed to osilodrostat. Robust statistical properties are also associated with this study design feature.

Participating institutions will be where the past treatment of patients took place using osilodrostat under ATU and/or as a part of routine clinical practice. Data will be abstracted from patients' existing electronic, or paper institutional medical records collected during the French ATU and/or routine clinical care. Importantly, the historical decisions of health care providers (HCPs) to treat patients with osilodrostat were made purely at the discretion of the treating physicians as discussed with their patients. Thus, there is no relationship between the decision to treat patients with osilodrostat and inclusion in this study.

The study schematic is presented in Figure 1 below and illustrates the dates corresponding to the study's retrospective follow-up period, the French ATU, the latest date an osilodrostat-treated patient is eligible for inclusion in the cohort study, and general timelines.

Final v2.0 34 of 63 18 April 2023

***at every 12 weeks until the earlier LFTU, death, or the end of the retrospective follow-up period or treatment discontinuation

Figure 1. Study Schematic

Abbreviations: ATU: Autorisation Temporaire d'Utilisation.; F/U: Follow Up; LTFU: Lost to Follow Up.

Clinical practice medical records will be reviewed for all eligible patients who received osilodrostat between April 2019 and the study start date at study sites in France. The study start date was the date the first site was initiated in the study, which was on 16 December 2022. The study will screen all patients at each site who were treated with osilodrostat in France within the frame of the ATU programme prior to commercial availability along with the patients who were treated with commercially available osilodrostat. All patients treated with osilodrostat between April 2019 and the study start date (16 December 2022) will be enrolled in the study.

Patients who have previously signed a general consent for research, either alive or deceased, can be enrolled with immediate effect. If no general consent was signed, a signed no-objection letter (NOL) will be requested from patients who are still alive. Some patients might not send the NOL back to the investigator. In such instance, the investigator can document a tacit approval from the patient if there is no response after a month of the first shipment of the NOL and after 3 documented contact attempts. For deceased patients since their past treatment with osilodrostat, they can also be enrolled after the investigator has checked that the deceased patient did not leave any written document stating refusal to participate in any scientific research.

Investigators will manually review and abstract clinical information from selected patients' medical records and will enter information into the electronic case report form (eCRF) from the date of initiating Osilodrostat through the follow-up period. All data are safeguarded using industry-best security practices to prevent unlawful disclosure and practices are compliant with Title 21 Part 11 policies of the Code of Federal Regulations. The HIMS software used for EDC purposes include password protection and encryption for all transmitted data. The platform will be approved by Recordati prior to study data abstraction or during site selection procedure.

The follow-up period will be variable, from the start of their osilodrostat onset period until the earlier of loss to follow-up, death, the end of the retrospective follow-up period or treatment discontinuation occurs. The patients with a potential follow-up of at least 12 weeks will be part of the primary analysis. The only patients excluded from the primary efficacy analyses will be the ones who started treatment with osilodrostat less than 12 weeks prior to the end of the abstraction period, and are still treated with osilodrostat at the end of the abstraction period. These patients will be included only in the analyses of the secondary and exploratory endpoints including safety. The patients who discontinued treatment for any reason or were lost-to-follow up prior to 12 weeks will be considered non-responders for the primary endpoint. The end of study is defined as the last available assessment after treatment initiation for the last patient.

The timing of data collection is summarised in the Figure 1/Table 2

Final v2.0 36 of 63 18 April 2023

Table 2 Data Collection Schedule

	Data Collection Points							
Assessment	BLa	Wk 4 ^b	Wk 8 ^b	Wk 12 ^b	Wk 18 ^b	Wk 24 ^b	Wk 36 and every 12 wks until death, loss to F/U or end of patient data collection*	
Window period		± 2	± 2	± 4	± 2	± 4	± 4 wks	
		wks	wks	wks	wks	wks		
Authorisation of access to patient's data for enrollment ^c	X							
Inclusion-Exclusion Criteria	X							
Demographics (age at diagnosis of CS, gender)	X							
BMI	X	X	X	X	X	X	X	
Clinical (disease) characteristics including date of diagnosis	X							
Medical and surgical history ^h	X ^g							
CS-Specific Physical Exam Findings (after BMI per every visit) [@]	X	X	X	X	X	X	X	

ECIOPP-RECAG-IVI-0390	Data Collection Points						
Assessment	BLa	Wk 4 ^b	Wk 8 ^b	Wk 12 ^b	Wk 18 ^b	Wk 24 ^b	Wk 36 and every 12 wks until death, loss to F/U or end of patient data collection*
Window period		± 2 wks	± 2 wks	± 4 wks	± 2 wks	± 4 wks	± 4 wks
Vital signs (blood pressure)	X	X	X	X	X	X	X
Electrocardiogram	X	X	X	X	X	X	X
Prior CS treatment(s)	X						
Prior medications ^e	X ^g						
Concomitant medications	X ^g	X	X	X	X	X	X
Osilodrostat initiating dose (date) ^d	X	X	X	X	X	X	X
Up /or down- titration regimen for Osilodrostat (date) ^d		X	X	X	X	X	X
Comprehensive Metabolic Panel (CMP&), Complete Blood Count (CBC*), lipids [§]	X	X	X	X	X	X	X
HBA1c	X	X	X	X	X	X	X

	Data Collection Points						
Assessment	BLa	Wk 4 ^b	Wk 8 ^b	Wk 12 ^b	Wk 18 ^b	Wk 24 ^b	Wk 36 and every 12 wks until death, loss to F/U or end of patient data collection*
Window period		± 2	± 2	± 4	± 2	± 4	± 4 wks
		wks	wks	wks	wks	wks	
Mean urinary free cortisol ^f	X ^g	X	X	X	X	X	X
Morning serum cortisol	X	X	X	X	X	X	X
Plasma Adrenocorticotropic hormone (ACTH), Serum 11- Deoxycortisol, Plasma 11- Deoxycorticosterone ,Plasma Aldosterone, Plasma Renin, Total Serum Testosterone or oestradiol (per patient sex), Serum LH, Serum FSH	X	X	X	X	X	X	X
Late night salivary cortisol	X	X	X	X	X	X	X

			D	ata Collec	tion Poin	nts	
Assessment	BLa	Wk 4 ^b	Wk 8 ^b	Wk 12 ^b	Wk 18 ^b	Wk 24 ^b	Wk 36 and every 12 wks until death, loss to F/U or end of patient data collection*
Window period		± 2 wks	± 2 wks	± 4 wks	± 2 wks	± 4 wks	± 4 wks
Adverse event	X	X	X	X	X	X	X
Osilodrostat discontinuation with reason for discontinuation		X	X	X	X	X	X

BL=Baseline

- a. At the time of osilodrostat initiation or the closest value within 2 weeks prior to osilodrostat initiation.
- b. Assessments at 4, 8, 12, 18, 24, 36 weeks will be collected, as well as all subsequent follow-up visits (at every 12 weeks until the earlier of loss to follow-up, death, or the end of the retrospective follow-up period or treatment discontinuation) under routine clinical practice, if available. The assessments which occurred closest to each defined visit should be recorded in the CRF, even if these assessments occurred on different dates.
- c. Either the patient has previously signed a general consent for research, or a signed no-objection letter (NOL) will be requested from the patient if still alive. If patient does not send the NOL back to the investigator, the investigator can document a tacit approval from the patient if there is no response after a month of the first shipment of the NOL and after 3 documented contact attempts. For a deceased patient since his/her past treatment with osilodrostat, access after the investigator has checked that this deceased patient did not leave any written document stating his/her refusal to participate in any scientific research.
- d. Osilodrostat initiation dose and up- and/or down-titration regimens (including dates) and reasons for titration will be recorded in the database during the study
- e. All prior medications taken within 6 months prior to the first dose of Osilodrostat must be collected.
- f. Baseline mean urinary free cortisol data can be collected within 1 month prior to osilodrostat initiation.

Final v2.0 40 of 63 18 April 2023

g. Footnote-a is not applicable to the following assessments: prior medications, concomitant medications, medical and surgical history, and mean urinary free cortisol.

- h. All available medical history and surgical history related to CS must be collected. Medical and surgical history not related to CS that occurred within 6 months prior to the first dose of Osilodrostat must be collected.
- *End of data collection may be due to earlier of loss-to-follow-up, death, end of retrospective follow-up period or treatment discontinuation

*CBC includes WBC, RBC, Haemoglobin, Haematocrit, MCV, MCH, MCHC, RDW, Platelet Count, MPV and Differential (Absolute and Percent - Neutrophils, Lymphocytes, Monocytes, Eosinophils, and Basophils)

&CMP includes Albumin, Alkaline Phosphatase, ALT, AST, Calcium, Carbon Dioxide, Chloride, Creatinine with GFR Estimated, Glucose, Potassium, Sodium, Total Bilirubin, Total Protein, (Blood) Urea Nitrogen

\$Lipid variables include Total Cholesterol, HDL, LDL, and Triglycerides

[@]For list of CS-specific examination findings, please refer to 8.3.2.

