8.7.5 Patient Disposition

The numbers and percentages of participants in each population will be tabulated. The reasons for participant exclusions from data analysis sets for each of the populations will also be tabulated. In addition, the number of participants who were treated, who died will be tabulated. Primary reasons for osilodrostat treatment discontinuation will be tabulated.

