10.1 Definitions

Adverse events (AEs)

An AE is any untoward medical occurrence in a patient or clinical study participant administered a pharmaceutical product, whether or not considered related to the product. An AE can therefore be any unfavourable and unintended sign (including an abnormal laboratory finding, for example), symptom, or disease (new or exacerbated) temporally associated with the use of a product.

Treatment-emergent adverse events (TEAEs)

Any AE with an onset date on or after the study drug start date and no later than 30 days after last dose of study drug, or any worsening of any AE on or after the study drug start date.

Serious adverse events (SAEs)

An SAE is any AE that:

- Results in death.
- Is life-threatening. (Note: The term 'life-threatening' in the definition of 'serious' refers to an event in which the subject was at risk of death at the time of the event; it does not refer to an event that hypothetically might have caused death if it were more severe).
- Requires inpatient hospitalization or prolongation of existing hospitalization.
- Results in persistent or significant disability/incapacity.
- Is a congenital anomaly/birth defect.

• Is an important medical event. Important medical events that may not result in death, be life-threatening, or require hospitalization may be considered an SAE when, based upon appropriate medical judgment, they may jeopardize the patient and may require medical or surgical intervention to prevent one of the outcomes listed in this definition.

Adverse drug reaction (ADR)

An ADR is defined as a response to a medicinal product which is noxious and unintended. Response in this context means that a causal relationship between a medicinal product and an AE is at least a reasonable possibility, i.e., the relationship cannot be ruled out.

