# 5.9 Safety Analysis

#### 5.9.1 Adverse Events

All AEs, whether they are serious/non-serious, related/unrelated, and all "special situations" reported in participants' charts within the data collection period should be collected. All AEs will be assessed according to incidence, grade, causality, outcome, action taken and seriousness.

TEAE and AESI were defined in section 5.3.3.5

An overview of adverse events will summarize the percentage of participants experiencing deaths, SAEs, AE reported as reason for discontinuation, TEAEs, and AEs possibly related to study drug.

The frequency and percentage of participants with following will be summarized using MedDRA preferred Term nested within SOC.

- TEAE
- TEAE by maximum severity
- TEAEs related to osilodrostat
- TEAE leading to osilodrostat dose interruption/adjustment
- TEAEs leading to study discontinuation
- SAEs including death
- SAEs by maximum severity
- SAEs related to osilodrostat
- Deaths
- AE of Special Interests (AESIs)

Project Document Version No.: 4.0; Document Effective Date: 30 October 2023

CONFIDENTIAL

RECORDATI AG, Rare Diseases Branch LCI699-RECAG-NI-0596

Statistical Analysis Plan

Adverse event summaries will be ordered in terms of decreasing frequency for SOC, and PT within SOC. For incidence counts, each participant will be counted only once within each Preferred Term and within each SOC. Percentages will be based on the number of participants in safety population. For events that are gender-specific, the denominator and computation of the percentage will include only participants from the given gender.

By-participant listings of all adverse events (including non-treatment-emergent events) recorded on the CRF, all TEATs, TEAEs leading to study discontinuation, SAEs including death, and deaths during the treatment period will be presented by participant, visit, preferred term, severity, and relationship to the study drug.

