#### 5.9.2 Deaths

A summary of all deaths and cause of death will be tabulated. The primary cause of death collected on the AE CRF page will be reported. If the primary cause of death is AE, the number of participants who have related AE and unrelated AE will be further reported.

A listing of all deaths will be provided.

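### Abstraction stops when osilodrostat is stopped, which conflicts with the protocol's 30-day treatment-emergent window and with death summaries that state no window, so deaths soon after stopping can be missed

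*Protocol*

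**What the plan says.** **When collection ends.** Protocol 8.1 has investigators abstract records from initiation through the follow-up period, which runs "until the earlier of loss to follow-up, death, the end of the retrospective follow-up period or treatment discontinuation occurs". A footnote to Table 2 repeats this for data collection: "End of data collection may be due to earlier of loss-to-follow-up, death, end of retrospective follow-up period or treatment discontinuation". SAP section 3 and its Table 1 carry the same rule.

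**Which adverse events are collected and counted.** SAP 5.9.1 says that events in the chart "within the data collection period should be collected", and its listing of deaths is confined to the treatment period. SAP 5.3.3.11 compares event start dates with an end bound that includes treatment discontinuation. Protocol 10.1 instead counts as treatment-emergent an event with onset "no later than 30 days after last dose of study drug".

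**What is promised on deaths.** Protocol 8.7.5: "the number of participants who were treated, who died will be tabulated". SAP 5.9.2: "A summary of all deaths and cause of death will be tabulated", with the cause taken from the adverse event CRF page. Neither gives a time limit. Among the research questions in Protocol section 7 is "What are the outcomes in these patients, including long term".

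**Deceased patients at enrolment.** Table 2 footnote c provides a route for patients who have died since treatment: "For a deceased patient since his/her past treatment with osilodrostat, access after the investigator has checked" that no written refusal of research was left.

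**The concern.** A safety table can contain only what was abstracted. If abstraction ends on the day the drug is stopped, a patient who stops and dies a week later may have no death record, and no rule applied at analysis can restore it. A reader of the report would still take a table of all deaths at face value.

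The cohort makes this more than a formality. It includes adrenocortical carcinoma and ectopic ACTH secretion, and Protocol section 6 says that ectopic disease has the worst prognosis. SAP 3.5 also defines a subgroup treated for under 12 weeks who had surgery and did not restart; a death around surgery, after the drug was stopped, falls after the cut-off. The study is meant to support a label expansion partly on safety, and omitted deaths can only lower the reported mortality.

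**Working it through.** The documents give no figure for this point that could be reproduced: the sample size of about 100 has no formula, and no expected death rate is stated. The check is therefore a comparison of the rules, followed by an illustration.

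**Step 1. Days after stopping that each rule covers**

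| Place | Purpose | Days after stopping |
|---|---|---|
| Protocol 8.1 and Table 2 footnote; SAP 3 and Table 1 | follow-up and data collection | 0 |
| SAP 5.9.1 | events collected; deaths listed | 0 (data collection period; treatment period) |
| SAP 5.3.3.11 | treatment-emergent events | 0 |
| Protocol 10.1 | treatment-emergent events | 30 after last dose |
| Protocol 8.7.5; SAP 5.9.2 | deaths reported | not stated |

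**Step 2. Which rule governs the data.** Protocol 10.1 classifies events; it does not tell sites to keep abstracting. The collection instruction is in 8.1 and Table 2, and it gives 0 days. The SAP drops the 30 days, and SAP 5.13 records no such change from the protocol. No text requires vital status, date of death or cause to be recorded after discontinuation. A site that follows 8.1 literally can close the record at the stop date, while a site that works from 10.1 may go on for 30 days.

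**Step 3. Illustration only; all death and discontinuation rates are assumed.** The intervals are Clopper-Pearson, the SAP's default for proportions: lower limit = 2.5% point of Beta(x, n − x + 1), upper limit = 97.5% point of Beta(x + 1, n − x), with n = 100. Start from 5 captured deaths and add missed ones.

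| Missed | Total | Rate (95% CI) |
|---|---|---|
| 0 | 5 | 5% (1.6–11.3%) |
| 1 | 6 | 6% (2.2–12.6%) |
| 3 | 8 | 8% (3.5–15.2%) |
| 5 | 10 | 10% (4.9–17.6%) |

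How many deaths could be involved? Let D patients stop, each with risk q of dying within 30 days. The expected number is D × q, and the chance of at least one is 1 − (1 − q)^D.

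- D = 20, q = 1%: 0.2 expected; 1 − 0.99^20 = 18%.
- D = 40, q = 5%: 2 expected; 1 − 0.95^40 = 87%.
- D = 60, q = 10%: 6 expected; 1 − 0.90^60 = 99.8%.

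The range is wide because nothing in the documents narrows D or q.

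**The case against.** The strongest reply is that the documents do not shut these deaths out. Protocol 10.1 puts a fatal event within 30 days of the last dose in scope. The death summaries have no limit. SAP 5.9.1 assesses the outcome of each event and also lists non-treatment-emergent ones, so an event that began on drug could carry a later fatal outcome. SAP 3.3 and 5.9.5 treat end of study and end of treatment as different dates and allow a change to 0 mg before end of study. The eCRF was not among the documents reviewed, so its adverse event page may reach further than the text does. All of this stands. A reader might infer that every death after stopping is excluded; the documents support only that its capture is not required and is left to inconsistent rules.

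A reader might also infer that sites already know whether each patient has died. They need not. Under Protocol 8.1, patients with a prior general consent are enrolled at once whether living or dead, and those enrolled by tacit approval are people who did not reply, whose status may be unknown. Nor does SAP 5.4 hold a separate count of the deceased to reconcile against: it has a mixed no-objection-letter waiver category that includes them. And knowing that a patient died does not put the date and cause in that hospital's chart.

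None of this supplies the missing instruction to abstract after discontinuation.

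**Conclusion.** The plan contradicts itself and should be corrected. The collection rule gives 0 days after stopping, the protocol's treatment-emergent definition gives 30, and the death summaries give no limit. Followed as written, the collection rule lets sites omit serious events and deaths that occur after the drug is stopped, and any such omission lowers the reported mortality and the count of fatal serious events.

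The direction follows from the rules; the size does not. The figures above rest on assumed numbers of deaths, discontinuations and 30-day risks, and they show only that a few missed deaths would visibly move a rate based on about 100 patients. The conclusion assumes that the eCRF follows the protocol text.

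**What to change.** 1. In Protocol 8.1, the Table 2 footnote, SAP section 3 and SAP Table 1, keep discontinuation as the end of effectiveness follow-up only. Extend abstraction of adverse events, serious adverse events and deaths to 30 days after the last dose, the limit that Protocol 10.1 already uses.
2. Align SAP 5.3.3.11 and 5.9.1, including the window for the death listing, with Protocol 10.1.
3. Record date and cause, where the chart gives them, for every patient known to the site to have died.
4. In SAP 5.9.2, show deaths on treatment, within 30 days of the last dose, and later as separate rows, and state that later deaths are incompletely ascertained.

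The cost is about 30 more days of chart review for each patient who stopped, a date-and-cause item and two extra table rows. The downsides are that later deaths will be incomplete and will largely reflect the underlying tumour, which is why they get their own row, and that the stated mortality may be less favourable. The change concerns data collection and reporting only.
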